**Confirmed**

**b. Is the research likely to have subjects who become prisoners while participating in the study?**

*For example, a longitudinal study of youth with drug problems is likely to have subjects who will be prisoners at some point during the study.*

	No
	Yes

\_\_\_\_\_

→ If yes, if a subject becomes a prisoner while participating in the study, will any study procedures and/or data collection related to the subject be continued while the subject is a prisoner?

 **No**  
 **Yes**

→ If yes, describe the procedures and/or data collection that will continue with prisoner subjects

**2.4 Protected populations.** IRB approval is required for the use of the subject populations listed here. Check the boxes for any of these populations that will be purposefully included. (In other words, being a part of the population is an inclusion criterion for the study.)

*The WORKSHEETS describe the criteria for approval but do not need to be completed and should not be submitted.*

Population	Worksheet
 Fetuses in utero	WORKSHEET: Pregnant Women
 Neonates of uncertain viability	WORKSHEET: Neonates
 Non-viable neonates	WORKSHEET: Neonates
 Pregnant women	WORKSHEET: Pregnant Women

a. If you check any of the boxes above, use this space to provide any information that may be relevant for the IRB to consider.

N/A

**2.5 Native Americans or non-U.S. indigenous populations.** Will Native American or non-U.S. indigenous populations be actively recruited through a tribe, tribe-focused organization, or similar community-based organization?

*Indigenous people are defined in international or national legislation as having a set of specific rights based on their historical ties to a particular territory and their cultural or historical distinctiveness from other populations that are often politically dominant.*

*Examples: a reservation school or health clinic; recruiting during a tribal community gathering*

 **No**  
 **Yes**

→ If yes, name the tribe, tribal-focused organization, or similar community-based organization. The UW IRB expects that tribal/indigenous approval will be obtained before beginning the research. This may or may not involve approval from a tribal IRB. The study team and any collaborators/investigators are also responsible for identifying any tribal laws that may affect the research.

**2.6 Third party subjects.** Will the research collect private identifiable information about *other individuals* from the study subjects? Common examples include: collecting medical history information or contact information about family members, friends, co-workers.

*“Identifiable” means any direct or indirect identifier that, alone or in combination, would allow you or another member of the research team to readily identify the person. For example, suppose that the research is about immigration history. If subjects are asked questions about their grandparents but are not asked for names or other information that would allow easy identification of the grandparents, then private identifiable information is not being collected about the grandparents and the grandparents are not subjects.*

No

Yes

→ If yes, these individuals are considered human subjects in the study. Describe them and what data will be collected about them.

**2.7 Number of subjects.** Is it possible to predict or describe the maximum number of subjects (or subject units) needed to complete the study, for each subject group?

*Subject units mean units within a group. For most research studies, a group will consist of individuals. However, the unit of interest in some research is not the individual. Examples:*

- Dyads such as caregiver-and-Alzheimer’s patient, or parent and child
- Families
- Other units, such as student-parent-teacher

*Subject group means categories of subjects that are meaningful for the specific study. Some research has only one subject group – for example, all UW students taking Introductory Psychology. Some common ways in which subjects are grouped include:*

- By intervention – for example, an intervention group and a control group.
- By subject population or setting – for example, urban versus rural families
- By age – for example, children who are 6, 10, or 14 years old.

*The IRB reviews the number of subjects in the context of risks and benefits. Unless otherwise specified, if the IRB determines that the research involves no more than minimal risk: there are no restrictions on the total number of subjects that may be enrolled. If the research involves more than minimal risk: The number of enrolled subjects must be limited to the number described in this application. If it is necessary later to increase the number of subjects, submit a Modification. Exceeding the IRB-approved number (over-enrollment) will be considered non-compliance.*

No → If no, provide the rationale in the box below. Also, provide any other available information about the scope/size of the research. You do not need to complete the table.

*Example: It may not be possible to predict the number of subjects who will complete an online survey advertised through Craigslist, but you can state that the survey will be posted for two weeks and the number who respond is the number who will be in the study.*

Yes

→ If yes, for each subject group, use the table below to provide the estimate of the maximum desired number of individuals (or other subject unit, such as families) who will complete the research.

Group name/description	Maximum desired number of individuals (or other subject unit, such as families) who will complete the research
------------------------	--

Provide numbers for the site(s) reviewed by the UW IRB and for the study-wide total number; example: 20/100	
Community health workers	3
Community based organization (CBO) administrators	3
Primary care and mental health providers	3
CBO participants for focus group	6
CBO participants for RCT	60

### 3 NON-UW RESEARCH SETTING

*Complete this section only if UW investigators and people named in the SUPPLEMENT: Non-UW Individual Investigators will conduct research procedures outside of UW and Harborview*

**3.1 Reason for locations.** Describe the reason(s) for choosing the locations.

*This is especially important when the research will occur in locations or with populations that may be vulnerable to exploitation. One of the three ethical principles the IRB must consider is justice: ensuring that reasonable, non-exploitative, and well-considered procedures are administered fairly, with a fair distribution of costs and potential benefits.*

This research is aimed at examining the feasibility of app-based screening and treatment of depression in women in rural settings with a high treatment gap such as at our India site.

**3.2 Local context.** Culturally appropriate procedures and an understanding of local context are an important part of protecting subjects. Describe any site-specific cultural issues, customs, beliefs, or values that may affect the research, how it is conducted, or how consent is obtained or documented.

*Examples: It would be culturally inappropriate in some international settings for a woman to be directly contacted by a male researcher; instead, the researcher may need to ask a male family member for permission before the woman can be approached. It may be appropriate to obtain permission from community leaders prior to obtaining consent from individual members of a group. In some distinct cultural groups, signing forms may not be the norm.*

*This federal site maintains an international list of human research standards and requirements:  
<http://www.hhs.gov/ohrp/international/index.html>*

Research will be conducted within CBOs, and consent will be obtained by community health workers who are known to the women. This approach has been used in previous studies in the same location and is acceptable to women and culturally appropriate.

Study procedures will be explained in detail before obtaining informed consent with the option of using thumb impression instead of signature if illiteracy is a barrier.

**3.3 Location-specific laws.** Describe any local laws that may affect the research (especially the research design and consent procedures). The most common examples are laws about:

- **Specimens** – for example, some countries will not allow biospecimens to be taken out of the country.
- **Age of consent** – laws about when an individual is considered old enough to be able to provide consent vary across states, and across countries.
- **Legally authorized representative** – laws about who can serve as a legally authorized representative (and who has priority when more than one person is available) vary across states and countries.
- **Use of healthcare records** – many states (including Washington State) have laws that are similar to the federal HIPAA law but that have additional requirements.

N/A

**3.4 Location-specific administrative or ethical requirements.** Describe local administrative or ethical requirements that affect the research.

*Example: A school district may require researchers to obtain permission from the head district office as well as school principals before approaching teachers or students; a factory in China may allow researchers to interview factory workers but not allow the workers to be paid for their participation.*

N/A

**3.5 If the PI is a student: Does the research involve traveling outside of the US?** N/A

No
Yes

→ If yes, confirm by checking the box that (1) you will register with the [UW Office of Global Affairs](#) before traveling; (2) you will notify your advisor when the registration is complete; and (3) you will request a UW Travel Waiver if the research involves travel to the [list of countries](#) requiring a UW Travel Waiver.

Confirmed
-----------

## 4 RECRUITING and SCREENING PARTICIPANTS

**4.1 Recruiting and Screening.** Describe how subjects will be identified, recruited, and screened. Include information about: how, when, where, and in what setting. Identify who (by position or role, not name) will approach and recruit subjects, and who will screen them for eligibility.

End user focus group: Women for the end user focus group will be recruited from via i) advertisements ii) flyers iii) word of mouth and iv) community health workers (CHWs). We will oversample for women with depressive symptoms such that we have an equal number of women with Patient Health Questionnaire -9 (PHQ-9) score above 5 and PHQ-9 score below 5. [For prescreening](#), to identify women with a PHQ-9 above 5, [community health workers located in the Community Based Organization \(CBO\) will use the PHQ-9 questionnaire](#), introduced with talking points which have been [uploaded](#).

Provider focus group: Primary care and mental health providers will be recruited from Anekal Primary Health Center and CHWs will be recruited from the Community Based Organizations (CBOs) and by contacting them through the parent Mahila Mandal Organization.

All advertisements and flyers will be reviewed and approved before use by the Human Subjects division at University of Washington.

For the RCT, participants will be recruited from community-based organizations (CBOs) via i) advertisements ii) flyers iii) word of mouth and iv) community health workers (CHWs). Our recruitment strategies will enable us to recruit women with varying degrees of depression and to be representative of women in the villages covered by the CBO.

All advertisements and flyers will be reviewed and approved before use by the Human Subjects division at University of Washington.

#### 4.2 Recruitment materials.

##### a. What materials (if any) will be used to recruit and screen subjects?

*Examples: talking points for phone or in-person conversations; video or audio presentations; websites; social media messages; written materials such as letters, flyers for posting, brochures, or printed advertisements; questionnaires filled out by potential subjects.*

Talking points for CHWs attached as appendix.

##### b. Upload descriptions of each type of material (or the materials themselves) to **Zipline**. If letters or emails will be sent to any subjects, these should include a statement about how the subject's name and contact information were obtained. No sensitive information about the person (such as a diagnosis of a medical condition) should be included in the letter.

*HSD encourages researchers to consider uploading descriptions of most recruitment and screening materials instead of the materials themselves. The goal is to provide the researchers with the flexibility to change some information on the materials without submitting a Modification for IRB approval of the changes. Examples:*

- *Provide a list of talking points that will be used for phone or in-person conversations instead of a script.*
- *For the description of a flyer, include the information that it will provide the study phone number and the name of a study contact person (without providing the actual phone number or name). This means that a Modification would not be necessary if/when the study phone number or contact person changes. Also, instead of listing the inclusion/exclusion criteria, the description below might state that the flyer will list one or a few of the major inclusion/exclusion criteria.*
- *For the description of a video or a website, include a description of the possible visual elements and a list of the content (e.g., study phone number; study contact person; top three inclusion/exclusion criteria; payment of \$50; study name; UW researcher).*

#### 4.3 Relationship with participant population. Do any members of the study team have an existing relationship with the study population(s)?

*Examples: a study team member may have a dual role with the study population (for example, being their clinical care provider, teacher, laboratory director or tribal leader in addition to recruiting them for his/her research).*

	No
	Yes

→ If yes, describe the nature of the relationship.

**4.4 Payment to participants.** Describe any payment that will be provided, including:

- The total amount/value
- Whether payment will be “pro-rated” so that participants who are unable to complete the research may still receive some part of the payment

*The IRB expects the consent process or study information provided to the subjects to include information about the number and amount of payments, and especially the time when subjects can expect to receive payment. One of the most frequent complaints received by HSD is from subjects who expected to receive cash or a check on the day that they completed a study and who were angry or disappointed when payment took 6-8 weeks to reach them.*

*Do not include a description of any expenses that will be reimbursed.*

Subjects will be compensated for their time spent on participating in the focus groups and individual interviews. All women (including CHWs and CBO attendees) will receive Rs. 200 (approx. \$3) each time they participate. This amount represents a payment for the time and potential stress associated with the study procedures and is comparable with other similar studies at this location. This amount of compensation is commensurate with the average income in this region and ensures that consent is not unduly influenced by financial consideration

**4.5 Non-monetary compensation.** Describe any non-monetary compensation that will be provided. Example: extra credit for students; a toy for a child. If class credit will be offered to students, there must be an alternate way for the students to earn the extra credit without participating in the research.

None

**4.6 Will data or specimens be accessed or obtained for recruiting and screening procedures prior to enrollment?**

*Examples: names and contact information; the information gathered from records that were screened; results of screening questionnaires or screening blood tests; Protected Health Information (PHI) from screening medical records to identify possible subjects.*

	No
	Yes

→ If no, skip the rest of this section; go to [question 5.1](#).  
→ If yes, describe the data and/or specimens (including PHI) and whether it will be retained as part of the study data.

For the CBO participant focus groups in Aim 1, potential participants will receive a paper based PHQ-9 to enable recruitment of up to 3 women with PHQ-9 scored of more than 5. The paper PHQ-9s will not have identifying information and will be shredded immediately after the CHW has determined the total scores. We will however maintain a count of how many women were prescreened and how many of them had a score of more than 5. For the RCT we will administer PHQ-9 to all attendees of the CBO using the same talking points, to identify CBOs with more than one woman who scores positive on the PHQ-9.

**4.7 Consent for recruiting and screening.** Will consent be obtained for any of the recruiting and screening procedures? ([Section 8: Consent of Adults](#) asks about consent for the main study procedures).

“Consent” includes: consent from individuals for their own participation; parental permission; assent from children; consent from a legally authorized representative for adult individuals who are unable to provide consent.

Examples:

- For a study in which names and contact information will be obtained from a registry: the registry should have consent from the registry participants to release their names and contact information to researchers.
- For a study in which possible subjects are identified by screening records: there will be no consent process.
- For a study in which individuals respond to an announcement and call into a study phone line: the study team person talking to the individual may obtain non-written consent to ask eligibility questions over the phone.

No

→ If no, skip the rest of this section; go to [question 5.1](#).

Yes

→ If yes, describe the consent process.

CHWs will administer the PHQ9, if more than one woman PHQ9 positive then CHW will proceed with informed consent for all members of SHG. The CHW will use the attached talking points to obtain verbal consent from participants.

a. Documentation of consent. Will a written or verifiable electronic signature from the subject on a consent form be used to document consent for the recruiting and screening procedures?

No

→ If no, describe the information that will be provided during the consent process and for which procedures.

Yes

→ If yes, upload the consent form to [Zipline](#).

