On repeat sign in, they will also receive questions on completion of behavioral activation homework. Women who score more than 15 will receive a prompt to view modules 1 through 4 which includes additional content on strategies for specific problems, and information on medications. They will receive information on how to seek mental health care. This ensures that women with mild to moderate depression receive initial treatment without having to overcome transportation barriers. The app will track, and graph PHQ-9 score change over time to inform need to step up care. Any woman who scores anything other than 0 on question 9 of the PHQ 9 (suicidal ideation item) will be asked to call the CHW associated with that CBO. For these women, the app will also trigger an alert to the CHW who will immediately call the patient to complete a risk assessment based on the study SI protocol. CHWs will be trained in the study safety protocol and a chain of contact will be established for each type of scenario. The woman will be escorted to the PHC if needed. Modules described above will follow the content of the Healthy Activity Program manual and will be delivered in

short (10-15 min) interactive multimedabased modules. Depending on their PHQ-9 score, women will watch 4 to 8 modules over the course of 1 to 3 months.

**Enhanced Usual Care (EUC):** For EUC, CHWs will offer standardized monthly group education (45 min) regarding the symptoms of depression, informed by training from study Investigators. All CHWs will receive education on depression symptoms and referrals.

**5.2 Recordings.** Does the research involve creating audio or video recordings?

	No	→ If no, go to question 5.3 .						

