**a. Is it anticipated that the research will produce any individual research results that are clinically actionable?**

“Clinically actionable” means that there are established therapeutic or preventive interventions or other available actions that have the potential to change the clinical course of the disease/condition, or lead to an improved health outcome.

In general, every effort should be made to offer results that are clinically actionable, valid and pose life-threatening or severe health consequences if not treated or addressed quickly. Other clinically actionable results should be offered if this can be accomplished without compromising the research.

	No
	Yes

→ If yes, answer the following questions (a.1-a.3).

**a.1. Describe the clinically actionable results that are anticipated and explain which results, if any, could be urgent (i.e. because they pose life-threatening or severe health consequences if not treated or addressed quickly).**

Examples of urgent results include very high calcium levels, highly elevated liver function test results, positive results for reportable STDs.

Research assessments include measures of depression which may indicate depression which will need treatment. We will inform subjects who score above the clinical cut off the results of their questionnaire and advise them to share these results with their primary care provider and seek treatment for depression. For all subjects, whether they score above the cut off or not, anyone who scores anything other than 0 on the 9th question of the PHQ-9 will be informed of this and will receive further assessment / intervention as outlined in the attached suicidality protocol.

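### The screening sections state no step for a non-zero PHQ-9 item 9, and the anonymous, shredded Aim 1 sheets leave nothing to follow up, although the plan elsewhere requires a response whatever the total score

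*Combined protocol and SAP*

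**What the plan says.** **The item-9 rule.** Section 5.1, describing the MITHRA app, says: "Any woman who scores anything other than 0 on question 9 of the PHQ 9 (suicidal ideation item) will be asked to call the CHW" for that CBO. The app also alerts the community health worker (CHW), who carries out a risk assessment. CHWs are to be trained in the safety protocol. Section 10.10 (a.1) is more general: "For all subjects, whether they score above the cut off or not, anyone who scores anything other than 0 on the" ninth PHQ-9 question is told of it and receives further assessment or intervention under an attached suicidality protocol.

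**Aim 1 screening (4.6).** "For the CBO participant focus groups in Aim 1, potential participants will receive a paper based PHQ-9", so that some women scoring above 5 can be recruited. Then: "The paper PHQ-9s will not have identifying information and will be shredded immediately after the CHW has determined the total scores". Two counts are kept: women prescreened, and women scoring more than 5.

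**RCT screening (4.6 and 4.7).** "For the RCT we will administer PHQ-9 to all attendees of the CBO using the same talking points", and the stated purpose is "to identify CBOs with more than one woman who scores positive on the PHQ-9". Section 4.7 adds: "CHWs will administer the PHQ9, if more than one woman PHQ9 positive then CHW will proceed with informed consent for all members of SHG". Verbal consent for screening is taken from the talking points.

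**The concern.** PHQ-9 item 9 asks about suicidal ideation, and the plan itself treats any answer other than zero as needing individual action, independently of the total. Screening is where the study puts that question to the most women, and most of them have not yet consented to the trial. The screening sections nevertheless use only a summary of the questionnaire: the total in Aim 1, and the number of positive women in the CBO for the RCT. If they are followed exactly as written, a disclosure can be made to study staff without any stated step attached to it. In Aim 1 the only document carrying the answer is then destroyed. What is at stake is the safety of women who are screened and not enrolled, and the study's ability to show afterwards that a disclosure was handled.

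**Working it through.** The plan gives no figure on this point, so the check is mainly a comparison of the sections.

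**1. What triggers action**

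| Place | Who is covered | What triggers action | Item-9 step stated? |
|---|---|---|---|
| 5.1, MITHRA app | Women using the app | Item 9 not zero | Yes: call, alert, risk assessment |
| 10.10 (a.1) | All subjects | Item 9 not zero, above or below the cut-off | Yes: suicidality protocol |
| 4.6, Aim 1 prescreen | Potential focus-group members | Total above 5 | No |
| 4.6 and 4.7, RCT screen | All CBO attendees | More than one positive woman in the CBO | No |

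**2. The total cannot stand in for item 9.** Taking the total as the sum of the items, a woman who answers 1 on item 9 and 0 elsewhere has a total of 1. She is below the Aim 1 threshold of 5, yet 10.10 covers her explicitly because its rule ignores the cut-off. Neither Aim 1 count would include her as a woman with a non-zero item 9.

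**3. What remains after Aim 1 screening.** No identifier is on the sheet, the sheet is destroyed once totalled, and only two counts are kept. Later tracing is impossible, and so is later proof that a hand-over took place. Action by the CHW while the woman is still present is not ruled out; it is simply not mentioned.

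**4. What is unstated for the RCT screen.** The text does not say whether these sheets are on paper, anonymous or destroyed. It says what follows when more than one woman is positive and nothing about a CBO with none or one. It also says nothing about item 9 for other women who are screened and not enrolled.

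**5. How many women are screened.** Six CBOs (1.5 and 5.1: three per arm) of about 15 to 20 members (1.8): 6 × 15 = 90 and 6 × 20 = 120. This assumes that every member attends. CBOs screened and not taken forward, and the Aim 1 prescreens, come on top.

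**6. Can a CBO be passed over?** The documents give no prevalence for a positive screen and no RCT cut-off, so the prevalence p is an assumption. If women are treated as independent, P(0 or 1 positive) = (1 − p)^n + n·p·(1 − p)^(n − 1).

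| Assumed p | n = 15 | n = 20 |
|---|---|---|
| 5% | 0.829 | 0.736 |
| 10% | 0.549 | 0.392 |
| 20% | 0.167 | 0.069 |
| 30% | 0.035 | 0.008 |

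A passed-over CBO is likely at low prevalence and rare at high prevalence. This shows only that the unstated case can arise. It says nothing about what happens to a woman with a non-zero item 9.

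**The case against.** The strongest reply is that silence in 4.6 and 4.7 does not mean that no response exists. The CHW administers the questionnaire and totals the Aim 1 sheets, so has the item-9 answer in hand before anything is shredded. The same CHWs are to be trained in the safety protocol, with a chain of contact for each kind of scenario (5.1). The form text that opens 10.10 says individual results may come from screening procedures, so its rule can be read as already covering the screen. The suicidality protocol, the talking points and the data and safety monitoring plan are uploaded separately and could contain the missing step.

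That reply stands against the stronger readings a reader might infer:

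- *Women flagged at screening get no response.* This is an inference from silence, and the documents that would settle it are not among those available.
- *RCT screening answers are shredded too.* Anonymity and destruction are stated only for Aim 1. Sharing the talking points does not mean sharing the sheet handling.
- *The problem is the lone positive woman in a passed-over CBO.* She is one example. Because the item-9 rule ignores the total, the gap concerns any screened woman who is not enrolled.
- *A woman excluded for a recent suicide attempt has no further contact.* In a qualifying CBO the CHW goes on to consent the whole group, and 8.2 describes contact by the CHW and the coordinator.
- *Subtracting 60 from the 90 to 120 gives the number never followed.* The 60 in 2.7 is a maximum for women completing the research. In addition, 5.1 makes the tablets available to all attendees at MITHRA CBOs, so an unenrolled attendee there may still reach the app alert.

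The reply does not remove the gap. Whether a woman screened before trial consent is a subject under 10.10 is unclear. If she is, anonymous sheets destroyed on totalling are hard to square with the rule. If she is not, the plan should say so openly. Either answer needs an edit.

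**Conclusion.** The concern holds as a failure to reconcile sections. The plan requires a response to any non-zero item 9 whatever the total, while its two screening procedures state no item-9 step. For Aim 1, the stated trigger for destroying the sheet is the total score, which leaves a flagged woman untraceable and her follow-up undocumented. That goes beyond missing detail. For the RCT screen, the defect is that sheet handling and the non-qualifying outcomes are left unstated.

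The gap covers every Aim 1 prescreen and roughly 90 to 120 women in the six CBOs if group sizes are as described and all members attend. The number of women with a non-zero item 9 cannot be derived, because the documents give no rate, and no estimate is offered. The conclusion rests on the text of 4.6, 4.7, 5.1 and 10.10 alone. It would narrow if the suicidality protocol or talking points turned out to cover screening, although the Aim 1 destruction wording would still need to agree with them.

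**What to change.** Before screening starts, reconcile 4.6 and 4.7 with 5.1 and 10.10:

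1. State whether the suicidality protocol applies to every PHQ-9 the study administers, including Aim 1 prescreening and RCT screening, and regardless of whether the woman is enrolled or the CBO qualifies.
2. Make the Aim 1 wording on anonymity and on the timing of destruction consistent with that answer.
3. State how RCT screening sheets are identified, kept and destroyed, and what is done with results from CBOs that have no or one positive woman.
4. Add the number of non-zero item-9 answers to the screening counts.
5. Align the talking points used for verbal screening consent.

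The clinical content of any response stays with the sponsor's suicidality protocol.

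The cost is a few sentences in two sections and in the talking points, plus one extra count. The CHW already administers the screen, so no new contact is needed to make the count. The drawback is that a flagged screening result may be briefly identifiable, which the verbal consent would have to say.
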